marketed or sold. The pilot study results may be used to inform the design of the future therapy device. The PI and Industry Sponsor are currently also writing an NIH translational development grant to further optimize the high-resolution therapy electrode and testing of the fully-implanted system.

[figure not shown]

Figure 2. A conventional, Permanent Electrode is shown on the left (Boston Scientific CoverEdge32) which provides 4 columns of stimulation contacts. The low-volume Study Electrode provides 8 columns of stimulation contacts for greater selectivity (8 x 8 high-resolution configuration).

B. STUDY DESIGN

1. Twenty patients offered SCS for standard of care will be invited to participate in this study. With the study electrode in place, we will be using intraoperative neuromonitoring per our routine standard-of-care. Demographic information will be collected including patient age (years), gender (male/female), duration of illness and medications with doses and frequency. Stimulator settings used for testing will be documented. Additional data about pain, disability and psychological status will be

collected prospectively at baseline. Peri-operative imaging will include standard of care pre-operative MRI/CT, intraoperative fluoroscopy, and post-operative scans.

Anesthesia type and routine somatosensory evoked potentials (SSEP) and motor evoked potentials (MEP) will be documented. Once intraoperative neuromonitoring is complete, the permanent electrode will be placed and programming will occur using the permanent electrode. Patients will fill out the following questionnaires to gauge pain level pre-operatively and postoperatively as per Prospective Observational Study of Outcomes following Neuromodulation for Pain InfoEd Study #3484: Numerical Rating Scale (NRS), McGill Pain Questionnaire (MPQ), Oswestry Disability Index (ODI), Pain Catastrophizing Scale (PCS), Beck Depression Inventory (BDI) and pain medication usage. Patients will return for a follow up programming session (with the implanted device) on post op day 1, and 3 months post-op as per standard of care. At these times patients will be asked to complete the outcome surveys listed above. The BDI tests for depression. If the research staff believes the patient may harm themselves based on their answers, the PI/treating physician will be notified, and help will be offered to them.

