The stimulation patterns and pulse patterns will be selected by the neurosurgeon to deliver stimulation therapy to the chosen electrode contact configurations (refer to Supplemental Materials Appendix C on stimulation contact configurations) estimated to provide selective dorsal column activation.

Approximately 10-20 electrode contact Groups will be performed during the study. Paresthesia maps will be created according to the region in which the neuromonitoring reports EMG activation.

Initially a central electrode bi-pole or tri-pole will be used, and the stimulus amplitude will be increased until neuromonitoring is used to identify an activation threshold (frequency will be fixed). At that time, 10-20 predefined stimulation electrode Groups will be stimulated (see Supplemental Material Appendix C for exemplar electrode patterns) at an amplitude below threshold. The various electrode Groups will be created using the Study Electrode in low-resolution and high-resolution configurations. Low-density electrode configurations will use 2 or more electrodes as a grouped-contact while high-resolution will use only one electrode. After the first group of stimulation contacts is activated, the EMG patterns will be recorded. Group 1 of stimulation contacts will be de-activated. A Group 2 of stimulation contacts will be activated, followed by recording the EMG responses. It may be necessary to alternate and re-activate Group 1 to verify repeatability. Group 3-Group 20 will be sequentially performed. This study procedure will be allowed for approximately 20 minutes, which should be

sufficient to collect the necessary data of high-resolution electrode contact patterns. A designated team member will record the EMG results (see case report form, Appendix A). Once the study data is collected, the Study Electrode will be removed from the subject.

< End of Study >

Step 4-b. Stimulation with Standard Electrode (Standard Procedure)

The procedure will continue as standard of practice. The Permanent Electrode will be placed and tested (Step 4) using the standard of care lateralization using Neuromonitoring. Once the location is confirmed, the Permanent Electrode may then be secured using sterile Nurolon suture per standard of care.

Step 5. Tunneling, Implant of the battery, and surgical closure (Standard Procedure)

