- iii. The proposed study will identify a paresthesia stimulation threshold, and then perform mapping between the dermatome where EMG-based Neuromonitoring demonstrates activation. Multiple Study Electrode contact Groups will be stimulated and recorded as to where the EMG recruitment is generated. The Groups will be designed to demonstrate selective stimulation, low-back stimulation, and bilateral paresthesia coverage. According to standard procedure, the Permanent Electrode is activated using multiple stimulation groups. Stimulation groups for the Study Electrode will be chosen such that at least two electrode Groups will be identical to those used for the Permanent Electrode. Additionally, the Study Electrode will be configured using low-density and high-resolution patterns as a direct comparison. The selectivity of paresthesia will be characterized for these Study Electrode configurations. The data will be analyzed to determine trends across subjects in whether the high-resolution stimulation improves the targeting of therapy to a focal number of dermatomes.

- iv. The study hypothesis is that the high-resolution Study Electrode will generate paresthesia that is focused to a more selective (smaller) dermatomal region than the currently available paddle electrodes according to the paresthesia maps. We further hypothesize that the Study Electrode will provide dorsal root activation and bi-lateral activation. We finally hypothesize that the Study Electrode may selectively provide paresthesia to the lower-back dermatomes. We do not believe that the Permanent Electrode will be able to achieve these outcomes.
- v. The study is designed to perform a relative comparison between high-resolution and low-density Electrode Groups using the Study Electrode. Repetitive stimulation contact Groups may be used (as defined in the protocol) to ensure repeatability of EMG responses. Statistical analysis of Study Electrode contact Groups will be explored but may not be statically significant as the exact surgical position of the electrodes will be different for each subject. The analyses will be compared between the stimulation amplitudes between the high and low-density Groups.
- vi. We will compute a dermatomal heat-map describing the stimulation dermatome observed by EMG. The 10-20 Groups of stimulation will allow us to answer the specific research questions:

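### One threshold, found on a central configuration, sets the amplitude for all Groups, so the high- versus low-density comparison mixes focality with effective intensity and item D.v has no response-defined amplitude to compare

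*Combined protocol and SAP*

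**What the plan says.** The procedure is in section B, Step 4-a. It opens with one configuration: "Initially a central electrode bi-pole or tri-pole will be used". The only ramp described is on that configuration: "the stimulus amplitude will be increased until neuromonitoring is used to identify an activation threshold". After that, "10-20 predefined stimulation electrode Groups will be stimulated (see Supplemental Material Appendix C for exemplar electrode patterns) at an amplitude below threshold", and the EMG pattern is recorded for each Group in turn. The two arms of the comparison are defined in the same step: "Low-density electrode configurations will use 2 or more electrodes as a grouped-contact while high-resolution will use only one electrode".

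Section D also speaks of one threshold. Item iii says "The proposed study will identify a paresthesia stimulation threshold", and later "The selectivity of paresthesia will be characterized for these Study Electrode configurations". Item v presents the high- versus low-density contrast within the Study Electrode as what the study is designed for, and adds: "The analyses will be compared between the stimulation amplitudes between the high and low-density Groups". It does not say whether this means applied amplitude, threshold amplitude or something else. Research question 2 (item viii) asks whether selectivity differs between the two configurations.

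Three other places bear on amplitude:
- Section B, item 1: "Stimulator settings used for testing will be documented".
- Study Pulse Generator System: amplitude ranges over 0 to 10 mA and moves 0.2 mA at a time.
- Figure 4 caption: amplitudes change together with the choice of contacts.

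The case report form (Appendix A) and the contact patterns (Appendix C) are not in the supplied text.

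**The concern.** Amplitude can enter this comparison as an input or as a response. Under Step 4-a it is an input, chosen by reference to a threshold measured on another configuration. A difference in applied amplitude between high- and low-density Groups then shows what the operator selected. It becomes a result only if it is tied to a response, such as the amplitude at which each Group first produces EMG activity.

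The same gap affects selectivity. The number of regions that respond rises with amplitude relative to a Group's own threshold. One contact and two or more ganged contacts need not share a threshold, and nothing in the plan equates them. The Group with the higher threshold is driven more weakly in effect and will tend to show fewer regions, or none. On a dermatomal map that can pass for focality.

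At stake are the contrast that item D.v names as the purpose of the design and the answer to research question 2. This is a bias, so more subjects would not remove it. Item D.x confines data capture to the intraoperative session, so thresholds not sought there cannot be recovered later.

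**Working it through.** **No figure to reproduce.** The documents give no power, effect size or threshold value for this comparison. The check compares the sections and adds simple arithmetic.

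**1. The sections side by side.** Step 4-a and item D.iii each describe one threshold. Step 4-a then places the Groups below it, at a level that is not stated and is not said to be common to all Groups. The Figure 4 caption implies that amplitude may differ by contact selection, but gives no rule. Re-activating Group 1, which Step 4-a allows, checks repeatability and does not match intensity between Groups.

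**2. Relative intensity.** Let f = common amplitude / central threshold and r = a Group's own threshold / central threshold. The Group is then driven at f/r of its own threshold. Both f and r are assumptions.

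| r | f = 0.9 | f = 0.8 |
|---|---|---|
| 0.5 | 1.80 | 1.60 |
| 0.8 | 1.125 | 1.00 |
| 1.0 | 0.90 | 0.80 |
| 1.25 | 0.72 | 0.64 |
| 2.0 | 0.45 | 0.40 |

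Values of 1 or more are at or above the Group's own threshold. Within one subject some Groups could respond while others stay silent, purely because of r. Read literally, an amplitude below threshold means that any Group with r of 1 or more is tested where no EMG activation is expected, although EMG activation is the outcome.

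**3. Illustration of the bias.** A simulation was run with no true difference in selectivity. Assumptions: 10 muscles, log-normal thresholds (log SD 0.30), noise (log SD 0.10), the same recruitment pattern in both Groups, and a common amplitude of 1.3 times the low-density Group's lowest threshold.
- High-resolution thresholds 10% higher: mean active muscles 2.9 (low-density) vs 1.9 (high-resolution); high-resolution looks more focal in 62% of subjects and less focal in 5%.
- 25% higher: 2.9 vs 0.9; more focal in 88%, less focal in 0.2%.
- 20% lower: 2.9 vs 5.2; less focal in 90%.
- Both at 1.3 times their own threshold: 2.9 vs 2.9; 33% each way.

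The 88% is inflated, because a silent high-resolution Group is scored as more focal. That happens in 24% to 37% of subjects, depending on whether the reference threshold is taken before or after noise.

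At 0.9 times the low-density Group's lowest threshold (taken before noise), the 25% case gives 0.19 vs 0.00 active muscles. High-resolution looks more focal in 18% of subjects, and the other 82% are ties with both Groups silent. At the same level with high-resolution thresholds 20% lower, it looks less focal in 87%.

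**4. Time for a threshold in every Group.** A full ramp has 10 / 0.2 = 50 increments. The 20 minutes are 1,200 s. With 10 Groups that is 120 s per Group, or 120 / 50 = 2.4 s per increment. With 20 Groups it is 60 s and 1.2 s. If ramps end at 5 mA (assumed, 25 increments), the times are 4.8 s and 2.4 s. Switching, repeats and the initial ramp are not counted.

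**The case against.** A reader might infer that amplitude is never measured per Group, that D.v has no outcome at all, or that the amplitude difference is zero by construction. The documents do not support this. Settings are to be documented, amplitude is adjustable in small steps, and the Figure 4 caption says it changes with the contacts. Appendix A is not available and may have a field for each Group; its absence here is not a fault of the plan. What stands is narrower: an amplitude field would record what was applied, and no supplied section describes a search for each Group's threshold.

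A reader might also take the 88% as the expected rate of false focality. That is not supported either. The simulation assumes stimulation above threshold where Step 4-a says below, it counts silence as focality, and it needs threshold ratios that the documents do not give. The mechanism survives at lower amplitudes, but its size changes greatly.

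Finally, item D.ii disclaims statistically valid results, item D.iii looks for trends, and item D.v calls the analysis exploratory. The heat-map and research questions 1 and 3 do not depend on the amplitude comparison. This lowers the severity. It does not answer the point, because D.ii still asks for meaningful endpoints that inform device development, and a trend confounded with intensity does not do that.

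**Conclusion.** The concern holds in a limited form. The plan describes one threshold on one configuration, says in another place that amplitudes change with contacts, and gives neither a threshold per Group nor a rule for equating intensity. D.v's amplitude comparison is therefore uninformative unless it uses a response-defined amplitude, and the selectivity comparison cannot separate focality from weaker effective drive.

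This rests on two assumptions: that regional spread increases with amplitude relative to a Group's own threshold, and that single and ganged contacts may differ in threshold. The bias works against whichever Group has the lower threshold. Which configuration that is, and by how much, cannot be derived from the documents, so the simulation figures are illustrations only. Severity is moderate: the defect touches the study's stated main contrast, but no formal test or decision rule depends on it.

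**What to change.** 1. Reconcile Step 4-a with the Study Pulse Generator System section and the Figure 4 caption on how amplitude is set for each Group. The level itself is for the investigator to decide.
2. For matched high-/low-density pairs, record each Group's own EMG activation threshold and the amplitude at which each further region joins. Do this within the investigator's existing amplitude limits and the 20-minute session.
3. Define D.v's amplitude outcome as the within-subject ratio of the paired thresholds. Treat Groups that do not reach threshold as censored at the highest amplitude applied.
4. Compare regions activated at the same multiple of each Group's own threshold, or compare the amplitude window between the first and second region. Do not compare regions at one common mA value.
5. Report Groups with no response separately, and do not count them as more focal.

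The text change is limited to protocol and case report form wording. The real cost is time. At 1.2 to 2.4 s per increment for full ramps in 10-20 Groups, matched pairs would have to run first, and fewer other Groups may fit in the session.
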